4.1 Selection of Study Population

Approximately 360 subjects will be enrolled at approximately 30 centres in the United Kingdom, European/Commonwealth countries and/or Costa Rica. Subjects will be enrolled only if they meet all the inclusion criteria and none of the exclusion criteria.

Deviations from the inclusion and exclusion criteria are not allowed because they can potentially jeopardize the scientific integrity of the study, regulatory acceptability, or subject safety. Therefore, adherence to the criteria as specified in the protocol is essential.

4.1.1 Inclusion Criteria

Each subject must meet all the following criteria to be enrolled in this study:

1. The subject is male or female 6 to 17 years of age, inclusive, on Day 1 (day of study vaccination).
2. The subject (and/or legal guardian) is capable of understanding the written informed consent, providing signed and witnessed written informed consent (or assent, depending on age), and understanding and complying with protocol requirements.
3. Female subjects of reproductive age must be nonpregnant and nonlactating, and if of childbearing potential (defined as any female who has experienced menarche at any time prior to or during the study), must agree to be heterosexually inactive from at least 21 days prior to enrolment and through 90 days following any study vaccination or agrees to consistently use any of the following methods of birth control from at least 21 days prior to enrolment and through 90 days following any study vaccination:
 - a) Condoms (male or female) with or without spermicide*
 - b) Diaphragm with or without spermicide*
 - c) Cervical cap with or without spermicide*
 - d) Intrauterine device

* **NOTE:** The highest level of protection is required, in accordance with local regulations.

- e) Oral or patch contraceptives
- f) Norplant®, Depo-Provera®, or other acceptable method of birth control that is designed to protect against pregnancy

NOTE: Periodic abstinence (eg, calendar, ovulation, symptothermal, post-ovulation methods) and withdrawal are not acceptable methods of birth control.

4. The subject has a stable health status, as established by physical examination, vital sign measurements (body temperature and heart rate), and medical history.
5. The subject (and/or legal guardian) has access to a consistent and reliable means of electronic or telephone contact, which may be in the home, workplace, school, or by personal mobile electronic device.
6. The subject is willing to refrain from routine nasal sprays (including steroid sprays) or washes for at least 7 days following any study vaccination.
7. The subject (and/or legal guardian) lives within a reasonable distance from the clinical site, is willing and able to travel to and from the clinical site for follow-up visits, and agrees to seek medical evaluation in the event of an AE requiring acute assessment.
8. The subject (and/or legal guardian) agrees to stay in contact with the clinical site for the duration of the study, has no current plans to move from the study area, and agrees to provide updated contact information, as necessary.

4.1.2 Exclusion Criteria

Subjects meeting any of the following criteria (by review of medical history and subject intake) will be excluded from the study:

1. The subject has a history of pertussis-containing vaccination (inclusive of school vaccination programs) or documented *B. pertussis* infection within 3 years prior to Day 1 and/or a history of Td-containing vaccination (without pertussis vaccine component) within 1 month prior to Day 1.

2. The subject has a chronic significant illness actively being treated or a history of recent intervention for worsening or fluctuating symptoms (at the discretion of the investigator).
3. The subject has a history of cancer (malignancy).
4. The subject has a congenital, hereditary, or acquired disease or disorder classified as autoimmune, immunodeficient, coagulopathy, hepatic, renal, neurologic (including a history of Bell's palsy), or moderate to severe cognitive. (Attention deficit hyperactivity disorder permitted.)
5. The subject currently uses smoking products (including vaping and e-cigarettes) and is unwilling to refrain from use from Day 1 through Day 29 following any study vaccination.
6. The subject has received immunoglobulin, blood-derived products, systemic corticosteroids (at a dose of >10 mg per day for more than 10 days), or other immunosuppressant drugs within 90 days prior to Day 1.
7. The subject has any chronic pulmonary disease requiring active medication or pulmonary therapies, with the following exceptions:
 - a) Subjects with exercise-induced bronchospasm, if currently well controlled, who are willing to refrain from intense exercise for 7 days following study vaccination or
 - b) Subjects with Step 1 (intermittent) asthma classification who have not had an exacerbation requiring oral systemic corticosteroids in the past year; have an FEV1 documented to be >80%; do not have restrictions in normal activity due to breathing issues; and have used a short-acting beta-agonist less than or equal to 2 days per week over the past 2 months.

NOTE: Subjects in the safety lead-in cohort are not allowed to have these exceptions.

8. The subject has a history of oro/nasopharynx surgery (eg, adenoidectomy, tonsillectomy) within 60 days prior to Day 1.
9. The subject has a known hypersensitivity to latex or any component of any study vaccine. Specific to Boostrix: the subject has known hypersensitivity to neomycin or

polymyxin; hypersensitivity after previous administration of diphtheria, tetanus, or pertussis vaccines; or has experienced transient thrombocytopenia or neurological complications following an earlier immunisation against diphtheria and/or tetanus.

10. The subject has participated in any other clinical trial for the testing of an unlicensed product where such product was received within 6 months prior to Day 1 or is planning to participate in any other clinical trial during study conduct through Day 85 following last study vaccination.

NOTE: Exceptions may be considered for an investigational COVID-19 vaccine if the product has entered into adult Phase 3 efficacy trials or is part of a mass vaccination rollout in this age group of subjects within a country. Direct guidance will be provided by the sponsor prior to study initiation.

11. The subject has routine and/or repeated contact with, or is currently living in a household with, an immunocompromised individual.
12. The subject has any medical condition that, in the opinion of the investigator, might interfere with the evaluation of the study objectives or might affect the safety of the individual (eg, eating disorder, major depression or anxiety disorder, history of alcohol or drug use).
13. The subject is a study team member or first-degree relative of a study team member.
14. The subject resides in a residence during the vaccination period (defined as through Day 85 following any study vaccination) where an infant less than 6 months of age resides or may reside.

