duration of 3 days, and was not associated with severe events. Re-vaccination/attenuated challenge did not result in worsening reactogenicity. Overall, the AE profile was similar between treatment groups and no SAEs were attributed to vaccination. The Phase 2b study was conducted in adults, in which the majority (>90%) was estimated to have received a whole cell pertussis (wP) vaccination as their primary vaccination series during infancy. In the current study, subjects will all have received aP vaccinations containing (at a minimum) PT, FHA, and PRN as their primary series and will have never received a wP vaccination. Since wP vaccines and BPZE1 induce Th1/Th17 responses, which have been associated with polarizing Th1 long-term immunity, whereas aP vaccines preferentially stimulates a polarizing Th2 pathways, administration of BPZE1 in this school-age population may be the first stimulation of the Th1/Th17 pathway for preferential T-cell-associated immunity (Warfel et al 2014; Antunes et al 2018).

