Acellular pertussis vaccines are currently recommended as both primary and booster vaccinations and usually given in a combination vaccine containing diphtheria (D/d), tetanus (T), and pertussis (P/p), with the level of antigen content dictated by standard nomenclature of DTaP (higher antigen content overall) or Tdap (lower antigen content for diphtheria and pertussis). The current recommendation in the United Kingdom includes the childhood booster of Tdap at 3 years of age with no adolescent booster of aP-containing vaccine, whereas some other European/Commonwealth countries and the US have a similar early childhood DTaP vaccination schedule but have added a Tdap booster during the school-age period (up to and including adolescence). This study will investigate BPZE1-induced immune responses in a background of DTaP or Tdap, with the last pertussis-containing booster occurring more than 3 years prior. BPZE1 alone as well as coadministration with Boostrix will be investigated to test safety and whether augmenting/broadening mucosal immune responses are possible in an aP primed-only population. Furthermore, the testing of interference of BPZE1 with all components found in Boostrix will be investigated as a key secondary objective. In addition, demonstrating protection against subsequent colonization using the attenuated challenge model (re-vaccination/attenuated challenge with BPZE1) will be investigated at 3 months following initial vaccination (optional substudy) as a secondary objective. As this population has never received a wP vaccination, this will be the first time that a broader immunization against *B. pertussis* is provided; therefore, additional hypotheses include the following: a single intranasal vaccination with BPZE1 will be sufficient to induce a differential immune response compared to Boostrix (eg, mucosal immunity induction and reduction in *B. pertussis* acquisition), and immunological boosting with re-vaccination/attenuated challenge is not required to achieve mucosal immunity and protection.

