6.2 Medical History

A medical history (including vaccination history, prior and concomitant medical conditions, and surgeries/significant procedures for medical conditions [eg, endoscopy, tonsillectomy]) will be collected at screening and reviewed and/or updated on Day 1 if screening occurs prior to Day 1.

Ideally, the subject will provide a vaccination card (or equivalent) or the subject's vaccination history can be accessed via a centralized vaccination register to record last known pertussis vaccination. If the subject's vaccination history is not available, the timing of prior pertussis vaccine may be estimated based on the national vaccination schedule appropriate for the age of subject.

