4.3.4. Per-Protocol (PP) Immunogenicity Analysis Set

Immunogenicity Analyses to be performed based on PP Immunogenicity Analysis Set.

The PP immunogenicity analysis set will consist of all subjects in the immunogenicity analysis set, with the following exclusions:

- Data from all available visits for subjects following the receipt of unsuitable investigational product (either via dispensed and/or assigned or delivered).
- Data from all available visits for subjects found to be ineligible at baseline per protocol.
- Data from all subjects who received at least one dose of whole-cell pertussis (wP) containing vaccine in their life.
- Data from all available visits for subjects following the use of major immune modulators or immunosuppressants or following the receipt of blood products.
- Data from all available visits for subjects following clinically significant protocol deviations that can affect the efficacy (immunogenicity) results as determined by clinical review.

- Data from any visit that occurs substantially out of window as defined by exceeding 30 days past the visit window or the time point whereby the follow-up visit should have occurred, whichever is most restrictive.
- For subjects in the colonization substudy, missing Day 92 and Day 99 cultures will be removed from the Colonization endpoint.

For analyses using the PP immunogenicity analysis set, subjects will be classified according to the randomized treatment group. Determination of exclusions from the PP Immunogenicity Analysis Set will be performed by the sponsor clinical lead in a blinded fashion prior to the database lock.

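### The protocol (v7.0) describes every subject as aP-primed and wP-naive, but no eligibility criterion enforces this; a wP-primed child could be enrolled and then leave the primary immunogenicity set, and no rule covers a never-vaccinated child

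*Protocol*

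**What the plan says.** **Stated population.** Protocol 1.1 says that "subjects will all have received aP vaccinations containing (at a minimum) PT, FHA, and PRN as their primary series" and that they "will have never received a wP vaccination". Protocol 1.2 repeats it: "As this population has never received a wP vaccination". Section 1.1 contrasts this with the adult Phase 2b study, where more than 90% were estimated to be wP-primed. It ties wP to Th1/Th17 responses and aP to Th2 responses.

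**Eligibility.** Neither the synopsis nor Protocol 4.1.1, 4.1.2 and 4.1.2.1 requires an aP primary series or excludes lifetime wP. Exclusion 1 begins "The subject has a history of pertussis-containing vaccination (inclusive of school vaccination programs) or documented" and covers pertussis vaccine of any type, or documented infection, within 3 years before Day 1. A Td clause covers the month before Day 1. Exclusion 15 concerns only pertussis vaccine received after enrolment, in substudy subjects.

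**Verification.** Protocol 6.2 prefers a vaccination card or register, and adds: "If the subject's vaccination history is not available, the timing of prior pertussis vaccine may be estimated based on the national vaccination schedule".

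**Analysis sets.** Protocol 7.3 has no wP exclusion in its per-protocol (PP) definition. SAP 4.3.4 adds one: "Data from all subjects who received at least one dose of whole-cell pertussis (wP) containing vaccine in their life". SAP 8 runs the immunogenicity analyses on the PP set, and SAP 8.1 makes it the estimand's target population. The Immunogenicity Analysis Set is used for sensitivity analysis. SAP 11 lists only the added 10 to 17 age group as a change. SAP 1 says that the SAP prevails over the protocol on planned analyses.

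**Time since last aP.** SAP 6.1 derives it from country and age alone, for example age minus 3 in the UK and age minus 4 in Costa Rica.

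**The concern.** Priming history is central to the question, because the study asks how aP-primed children respond to their first broader pertussis immunization. A site, however, screens against criteria and not against the background section. The criteria as written admit two kinds of child whom the background says are absent.

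- **wP-primed, last dose more than 3 years ago.** Such a child is randomised and vaccinated, then removed from the set that answers the primary immunogenicity and key secondary questions. Nothing in the sample size allows for that loss.
- **Never given any pertussis vaccine.** Such a child breaches no criterion and stays in the PP set, so a first response could be mixed into estimates described as booster responses. SAP 6.1 would also assign an interval since an aP dose that was never given.

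**Working it through.** **1. Tracing the rules (v7.0 and SAP)**

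| Child | Exclusion 1 | PP set | Primary safety and Immunogenicity-set sensitivity analyses | Time since last aP (SAP 6.1) |
|---|---|---|---|---|
| aP-primed, last dose over 3 years ago | passes | in | in | schedule value |
| wP dose over 3 years ago | passes | out (wP rule) | in | schedule value |
| Never vaccinated | passes | in | in | schedule value, though no dose was given |

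The PP rule "Data from all available visits for subjects found to be ineligible at baseline per protocol" does not reach the last row, because no criterion was breached. The PP rule on clinically significant deviations does not reach it either, because there was no deviation. That these children stay in is inferred from the absence of a rule; no passage says so.

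**2. Reproducing the plan's power** (Protocol 7.1; SAP 4.1 and Table 4-2)

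- Evaluable n per group: 120 × 0.90 = 108.
- Primary: paired t-test, effect size 0.35, two-sided 0.05. Power = 1 − F(t₀.₉₇₅; df = n − 1, ncp = 0.35√n), with F the noncentral t distribution function. At n = 108, ncp = 3.64 and power = 0.950. Joint power = 0.950² = 0.902. The stated 95% and 90% are reproduced.
- PRN non-inferiority: two-sample t-test, difference −0.075, SD 1.4363, margin −0.693, one-sided 0.025. ncp = (−0.075 + 0.693) / (1.4363 × √(2/108)) = 3.16, and power = 0.883. The stated 88% is reproduced.

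**3. Illustration of the loss**

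The documents give no wP frequency, so a fraction w is assumed. The 10% covers dropout only, so wP exclusions come out of the 108: n = 108 × (1 − w), rounded down.

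| Assumed w | PP n per group | Power, each primary test | Joint primary power | PRN power |
|---|---|---|---|---|
| 0 | 108 | 95.0% | 90% | 88% |
| 5% | 102 | 93.8% | 88% | 86% |
| 10% | 97 | 92.7% | 86% | 85% |
| 20% | 86 | 89.4% | 80% | 80% |

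The PRN column follows the plan's own two-sample calculation. SAP 8.2 analyses PRN by ANCOVA with baseline IgG, so the actual power may differ.

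No size can be given for never-vaccinated children. The documents give neither their frequency nor how far their response would differ.

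**The case against.** The best defence is that choice of country and age was meant to do this work. Protocol 1.2 says that most developed countries moved to aP about two decades ago, and subjects are aged 6 to 17. On that view exceptions are rare and the SAP's wP rule is a backstop. This stands as a reason to expect small numbers. It does not show that there are none, and the SAP would need no lifetime-wP rule if exceptions were impossible.

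Other points stand:

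- The optional blinded sample size recalculation (Protocol 7.2) looks at data completeness and drop-out, so some loss could be noticed. It is optional, and priming history is not among its inputs.
- Protocol 6.2 allows only the timing of a past dose to be estimated. A reader might infer that vaccine type may be taken from the schedule too, but the text does not say so.
- For the Boostrix antigens, randomisation balances unprimed children in expectation. SAP 8.2 adjusts PT, FHA and PRN for baseline IgG.
- The schedule-based interval feeds a baseline summary and a median-split subgroup (SAP 8.3.1, 8.3.2), not the primary test.
- Demanding card or register proof would turn away children whom 6.2 deliberately accommodates, so it is a debatable trade-off.

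**Conclusion.** The point holds as an inconsistency between the population stated, the one the criteria admit and the one analysed. The SAP's wP exclusion is missing from Protocol 7.3 and unlisted in SAP 11, and the sample size does not allow for it. Never-vaccinated children fall under no rule.

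The size is unknown and may be small. At an assumed 5% wP-primed, joint primary power is about 88% against 90%, a minor loss. At 20% it is about 80%, and PRN power is also about 80%. These fractions are assumptions, not estimates from the documents.

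Three stronger readings are tempting but unsupported:

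- **That such children were enrolled.** The documents show only that they could be.
- **That wP-primed children add nothing to the primary answer.** Reactogenicity is also a primary endpoint and is analysed on the Safety Analysis Set, where they count. They also count in the Immunogenicity-set sensitivity analyses, where their presence is no flaw.
- **That the exclusion biases the treatment comparison.** wP history predates randomisation, and SAP 4.3.4 has PP exclusions decided blinded before lock.

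The finding is limited to protocol v7.0. SAP 1 cites a 10OCT2023 version for Costa Rica only, which was not supplied.

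**What to change.** 1. **Protocol 4.1.1, 4.1.2 and synopsis:** exclude any known prior wP-containing dose and require a history of an aP primary series. Use the history already collected under 6.2, from a card or register where available, without making documentary proof mandatory.
2. **Protocol 7.3 and SAP 4.3.4:** reconcile the two PP definitions and list the wP exclusion in SAP 11.
3. **SAP 4.3.4, before lock and while blinded:** add a PP exclusion for subjects known to have had no aP primary series.
4. **SAP 6.1:** do not assign those subjects a schedule-based time since last aP.
5. **Reporting:** give counts of wP-primed and unprimed subjects by arm.

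The cost is a few lines of text and no new data collection. A few children would be turned away at screening, and the PP n may be slightly smaller if unprimed subjects are already enrolled.

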4.1.2.1 Additional Exclusion Criteria (Substudy Subjects ONLY)

Subjects meeting any of the following criteria will be excluded from participation in the optional substudy (Section 3.1.1):

15. Has received a pertussis-containing vaccination outside of study conduct since enrollment.
16. Has received any form of immunotherapy determined to potentially have an effect on immune response (as determined by medical consultation, when necessary).

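### Exclusion 8 bars recent nose or throat surgery only before the Day 1 dose; no named rule covers the Day 85 substudy dose of the same live intranasal vaccine

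*Protocol*

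**What the plan says.** Protocol section 4.1.2, criterion 8 reads: "The subject has a history of oro/nasopharynx surgery (eg, adenoidectomy, tonsillectomy) within 60 days prior to Day 1". Section 5.2 gives every substudy participant a second intranasal application of 10^9 CFU BPZE1 on Day 85, with the same dose, volume and route as the BPZE1 given on Day 1. Section 3.1.1 caps the substudy at 120 children and lets the Day 85 dose be deferred by up to 20 days.

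Table 13-1 schedules a review of the inclusion and exclusion criteria at SSV3 (Day 85), before the dose. Section 4.1.2.1 adds two substudy exclusions. Criterion 15 is "Has received a pertussis-containing vaccination outside of study conduct since enrollment". Criterion 16 is "Has received any form of immunotherapy determined to potentially have an effect on immune response (as determined by medical consultation, when necessary". The holds in section 4.1.3 apply to both dosing days and cover respiratory symptoms, fever, antibiotics, a recent licensed vaccine and a positive SARS-CoV-2 test. Surgery appears in neither list.

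Other criteria are tied to every dose. Inclusion 6, for example, reads "The subject is willing to refrain from routine nasal sprays (including steroid sprays) or washes for at least 7 days following any study vaccination".

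**The concern.** The sponsor thought recent surgery of the nose or throat important enough to bar the first intranasal administration at every site. The second administration uses the same live organism, dose and route, but the rule does not follow it. Take a child who has a tonsillectomy on Day 70. No criterion names that event, and the child may be dosed 15 days later. The same operation 15 days before Day 1 would have barred the first dose.

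The protocol gives no reason for criterion 8. If the reason is safety, the second dose raises the same question. If it is the quality of the nasal readouts, section 3.1.1 gives the second dose its own 7-day nasal/respiratory diary, swabs on Days 92 and 99 and a nasal sample on Day 113. That either reason carries over is inference, though a natural one.

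What is at stake is consistent protection of substudy children. Section 4.1 allows no deviation from the criteria, so a named rule binds all of the approximately 30 centres. Without one, the decision rests on local judgement.

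**Working it through.** The plan gives no figure on this point, so there is none to reproduce. The check compares the criteria and then does date arithmetic.

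**Step 1. Exclusions counted back from Day 1, and what replaces each at Day 85.** There are four in section 4.1.2.

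| Exclusion | Look-back from Day 1 | Named cover at Day 85 | Not named |
|---|---|---|---|
| 1: pertussis vaccine or infection; Td | 3 years; 1 month | Criterion 15 (vaccination); 14-day vaccine hold (4.1.3); Td only in emergency during the first 90 days (5.7) | Documented *B. pertussis* infection after Day 1 |
| 6: immunoglobulin, blood products, steroids, immunosuppressants ("or other immunosuppressant drugs within 90 days prior to Day 1") | 90 days | Criterion 16 (immunotherapy, no time limit) | A qualifying steroid course; blood products |
| 8: oro/nasopharynx surgery | 60 days | None | All of it |
| 10: other trials | 6 months | Own forward clause: "is planning to participate in any other clinical trial during study conduct through Day 85 following last study vaccination" | The clause concerns planned participation, not product already received |

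Exclusion 8 is the only one of the four with no named counterpart at all.

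**Step 2. The exclusion 8 window.** Inputs: a 60-day look-back (4.1.2), a dose on Day 85 (5.2), and deferral to Day 85 + 20 = Day 105 at the latest (3.1.1). Surgery is inside the window if dose day − surgery day ≤ 60.

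- Dose on Day 85: 85 − 60 = 25, so surgery on Days 25-84. That is 60 of the 84 days from Day 1 to Day 84 (71%).
- Dose on Day 105: 105 − 60 = 45, so surgery on Days 45-104. That is 60 of 104 days (58%).
- In both cases all 60 days fall after Day 1, so the present wording covers none of them.

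**Step 3. What deferral could clear.** The first permitted dosing day is surgery day + 61. To dose by Day 105, surgery must fall no later than 105 − 61 = Day 44.

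- Days 25-44: 20 of 60 days (33%) can be cleared by deferral.
- Days 45-84: 40 of 60 days (67%) cannot, and the child would leave the substudy.
- Surgery on Day 70: 85 − 70 = 15 days before a Day 85 dose and 105 − 70 = 35 days before a Day 105 dose. The first permitted day would be 70 + 61 = Day 131.

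**Step 4. Exclusion 6 on the same basis.** With a 90-day look-back, every exposure on Days 1-84 lies inside the window for a Day 85 dose. Deferral clears exposures up to 105 − 91 = Day 14, which is 14 of 84 days (17%). This matters only for exposures that no other criterion already bars.

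These are window lengths, not event rates.

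**The case against.** The strongest reply is that the second dose is not unguarded. The criteria are reviewed afresh at SSV3, and several are undated. Inclusion 4 requires stable health. Exclusion 2 reaches "a history of recent intervention for worsening or fluctuating symptoms (at the discretion of the investigator", which could fit a tonsillectomy for recurrent symptoms. Exclusion 12 covers any condition that the investigator thinks could affect safety or the evaluation. Section 6.3.5.2 foresees vaccination delay for a medical condition determined by the investigator. The antibiotic and respiratory-symptom holds may also catch some children after an operation. All of this stands. A reader might infer that nothing could stop the dose, and the documents do not support that. But these provisions are general, discretionary or incidental, and none requires a site to wait 60 days.

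A reader might also infer that surgery would go undetected, because medical history is not scheduled at SSV3. That is not supported either. Section 6.3.5.3 treats medical history as conditions present at screening. Section 6.3.5.2 has every visit ask about hospitalisation and new medications, and SSV3 has a concomitant-medication check before the dose.

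The exclusion 6 gap is narrow. Criterion 16 has no time limit, so for what it covers it is stricter than 90 days. Exclusions 3 and 4 and the asthma condition in 7b ("have not had an exacerbation requiring oral systemic corticosteroids in the past year") cover many of the other cases. What remains is mainly a steroid course for another reason, or a blood product.

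Finally, it would be wrong to present surgery as the only gap. A documented *B. pertussis* infection after Day 1 is not named either, and it bears directly on a colonisation challenge.

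**Conclusion.** The point holds as a minor safety and consistency correction to the optional substudy. Exclusion 8 has no named counterpart for the Day 85 dose. After surgery on Days 25-84, only inclusion 4 and exclusions 2 and 12 could stop dosing as a matter of eligibility. Exclusions 1 and 6 are carried over in part, with the smaller gaps shown in the table.

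At most 120 children receive the second dose. The documents give no rate for surgery, steroid courses, blood products or interval infection, so the number affected cannot be estimated; it is likely to be small.

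A reader might infer that the colonisation or immunogenicity results are biased. The documents do not support that. The primary and key secondary endpoints are read at Day 29, before the second dose. Nothing in the documents indicates that post-surgical children would shift the colonisation results. SAP section 4.3.4 already drops per-protocol data after immunosuppressants or blood products, although that is an analysis rule and does not govern dosing.

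The conclusion assumes that criterion 8 is read as worded and applies to Amendment 6 (v7.0). SAP section 1 mentions a later version for Costa Rica only, which is not among the documents, so nothing is asserted for those sites.

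**What to change.** Reword exclusion 8 to *within 60 days prior to any study vaccination*, or repeat it in section 4.1.2.1 counted back from the actual Day 85 dose. Allow deferral within the existing 20 days where that clears the window. In the same edit, re-anchor exclusion 6 in the same way and add documented *B. pertussis* infection since enrolment to 4.1.2.1. Sites would confirm all three at the criteria review already scheduled at SSV3, so no medical-history item or other new procedure is needed.

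The cost is two criteria reworded and one added, with a few substudy children dosed later or lost. Sample size and the planned analyses do not change, and no extra sensitivity analysis is called for.
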